## Protocol: Glial Regulators for Testing Comorbid Posttraumatic Stress Disorder and Substance Use Disorders

total number of standard drinks consumed and the OCDS total score as the primary outcomes. A Poisson distribution will be assumed with a logarithm link function to assess the effects of NAC treatment. Data collected in substance abuse studies often contain a preponderance of zeros, and these zeros in the distribution can be considered sampling zeros in the Poisson process (Bandyopadhyay et al., 2011). If this excess is present in the distribution, two-part Hurdle models (Poisson and NB) will be explored (Cragg et al., 1971). The hurdle part of the model will allow us to estimate the probability of abstinence during the study period (as an odds ratio) while the Poisson/NB portion will allow for the assessment of the risk of an increase in using days beyond zero during the study period (as a risk ratio). Baseline alcohol/substance use and craving will be included in pertinent models as covariates. Additional alcohol/substance use outcomes will be assessed: change in percent drinking days, percent heavy drinking days, EtG, and VAS craving levels.

Hypothesis 2: NAC treatment will result in significantly greater reduction in PTSD severity (CAPS-5) as compared to placebo. To test this hypothesis, generalized linear mixed effects regression models with a Gaussian distribution will be developed to assess group differences while adjusting for baseline CAPS-5 scores. Assumptions of residual normality and homoscedasticity will be checked using statistical test and graphical methods (Residual and Q-Q plots, and Shapiro-Wilk tests) and transformation will be done as necessary. Restricted maximum likelihood methods will be used to estimate the fixed effects and variance components. Additional outcomes (e.g., PCL-5, CAPS-5 symptom subscales) will be examined.

Hypothesis 3A: Prefrontal cortex-amygdala connectivity at rest and in response to alcohol/drug vs. neutral cues will predict reduction in alcohol/substance use severity (total standard drinks).

Hypothesis 3B: Prefrontal cortex-amygdala connectivity at rest and in response to trauma vs. neutral cues will predict reduction in PTSD severity (CAPS-5).

For hypotheses 3A and 3B, the following preprocessing and analytical parameters will be used. Preprocessing: Post-acquisition preprocessing and statistical analysis of imaging data will be performed using FEAT (FMRI Expert Analysis Tool) Version 5.98, part of FSL (FMRIB's Software Library). Data will be preprocessed using scripting tools from FEAT. Non-brain signal will be removed using FSL's BET brain extraction. Scans will be corrected for motion using FSL's linear registration and scans will be spatially smoothed. Participants with head motion  $\geq 0.2$  mm will be excluded from the analyses (Power et al., 2012). Motion artifacts will be identified and scrubbed from each subject's data. Scans will be spatially co-registered with a standardized anatomical template (Montreal Neurological Institute) using a 12 parameter affine transformation. Analysis: Functional connectivity will be measured using a psychophysiological interaction (PPI) seed-based approach (Friston et al., 1997). PPI analysis is used to assess the functional coupling between different brain regions. The PPI is defined as the change in connectivity of one area (i.e., the seed region) to another in relation to the experimental context (e.g., alcohol vs. neutral cues). PPI analyses for resting state, trauma and alcohol/drug cues will be performed separately. Customized sq. wave forms representing the trauma run (1=trauma block and -1=neutral block) and the alcohol/drug cue run (1=alcohol/drug block and -1=neutral block) will be convolved with a double-gamma hemodynamic response function. A mask of the seed region will be made using a 12-mm diameter sphere located in the center of the AMY using the MNI coordinates (x, y, z =  $\pm 22, 0, -22$ ). The transformation parameters described above will also be applied to the mask. For each subject, the mean corrected and high pass filtered time series of the BOLD signal in the AMY will be extracted and used in a single subject whole brain PPI analysis. The PPI model will include the task vector, time series of the BOLD signal in the AMY, a term representing the positive task x seed interaction, and a term representing the negative task x seed interaction. The first level analysis will generate contrast images of the parameter estimates for each of the four regressors. Voxels will be thresholded at  $Z > 2.3$  using a corrected cluster threshold of  $p=0.05$ . The contrast images of the parameter estimates of the positive and negative task x seed interactions will be combined for group-level t-tests to identify regions that exhibited altered connectivity with the AMY during the trauma and alcohol/drug cues as compared to neutral cues. All group-level results will be thresholded at  $Z > 2.3$  using a corrected cluster threshold of  $p=0.05$ . Separate linear regression tests will be used to test for associations between PFC-AMY connectivity at baseline and improvement in AUD/SUD and PTSD symptoms during treatment. Changes in total standard drinks will be

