## Protocol: Glial Regulators for Testing Comorbid Posttraumatic Stress Disorder and Substance Use Disorders

### Hypotheses

Hypothesis 1: Participants receiving N-acetylcysteine (NAC), as compared to placebo, will demonstrate significantly greater reduction in SUD severity and craving from baseline to end of treatment (week 8).

Hypothesis 2: Participants receiving N-acetylcysteine (NAC), as compared to placebo, will demonstrate significantly greater reduction in PTSD severity from baseline to end of treatment (week 8).

Hypothesis 3: Prefrontal cortex-amygdala connectivity at rest and in response to cues will predict reduction in SUD and PTSD severity.

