### METHODS

**Overview:** A randomized, double-blind, placebo-controlled clinical trial among individuals (N=90) with SUD and PTSD will be conducted to test the hypothesis that N-acetylcysteine (NAC) will significantly reduce SUD severity, craving, and PTSD symptoms. A subset of enrolled subjects between the ages of 21-40 will complete neuroimaging procedures before and after treatment. All procedures will be reviewed by the MUSC IRB and the Ralph H. Johnson VA Research and Development committee prior to study start.

**Participants:** Ninety male and female participants between the ages of 18 to 75 with current AUD/SUD and comorbid PTSD or sub-threshold PTSD will be recruited to participate in the study.

**Recruitment:** Primary recruitment sites include (1) the Ralph H. Johnson VAMC outpatient Substance Treatment and Recovery Clinic (STAR) and (2) the PTSD Clinical Team (PCT).

**Inclusion/Exclusion Criteria:** To be included, subjects must (1) be 18-75 years old, (2) meet DSM-5 criteria for current PTSD or subthreshold PTSD, and (3) meet DSM-5 criteria for current AUD/SUD. Exclusion criteria include: (1) schizophrenia, bipolar disorder or an eating disorder; (2) any significant medical illness (e.g., asthma) that may adversely affect safety or study participation; (3) psychotropic medication initiation within 4 weeks of study participation or use of the following medications: carbamazepine, phenytoin, nitrous oxide, methotrexate, 6-azauridine triacetate, nitroglycerin or any other medication that may have an adverse interaction with NAC; (4) pregnant or nursing women; and (5) clinically significant suicidal ideation and intent.

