### **General Diagnostic and Inclusion/Exclusion Criteria**

- Demographics and Military Service Characteristics Form: This form measures demographics (e.g., age, race, gender, education, marital status) and military service information, such as branch and rank.
- Treatment Services Review: This form obtains information about the participant's ongoing/new treatment for alcohol/substance use and PTSD.
- Mini International Neuropsychiatric Interview 7.0 (MINI 7.0; Sheehan et al., 1998): The MINI will be used to diagnose AUD, SUD, and confirm other exclusionary psychiatric diagnoses.
- History of Head Injuries: A questionnaire that will be administered at Baseline, and Week 8 for anyone participating in fMRI, to assess for head injuries.

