**Table 1. Assessment Instruments and Timeline**

Instrument	Baseline	Medication Initiation	Medication and Symptom Monitoring								Follow Up
	Weeks → -1	0	1	2	3	4	5	6	7	8	1 & 3 Mth
Demographic Data	X										
History and Physical Examination	X										
MINI Diagnostic Interviews	X										
Concurrent Medications Form	X	X	X	X	X	X	X	X	X	X	X
Vital Signs	X					X				X	
Medication Log		X	X	X	X	X	X	X	X	X	
Urine Pregnancy Test for Females	X					X				X	
Urine Drug Screen: UDS	X					X				X	X
Riboflavin Test		X				X				X	
Adverse Events		X	X	X	X	X	X	X	X	X	X
Breathalyzer/Saliva BAC Tests	X	X	X	X	X	X	X	X	X	X	X
Timeline Follow- Back: TLFB	X	X	X	X	X	X	X	X	X	X	X
CIWA-AR	X										
Visual Analog Scales; VAS	X	X	X	X	X	X	X	X	X	X	X
Obsessive Compulsive Drinking Scale: OCDS	X	X	X	X	X	X	X	X	X	X	X
Ethyl glucuronide (EtG)		X				X				X	X
Clinician Administered PTSD Scale: CAPS-5	X					X				X	X
PTSD Checklist: PCL-5	X		X	X	X	X	X	X	X	X	X
Life Events Checklist: LEC-5	X										
Childhood Trauma Questionnaire: CTQ-SF	X										
Beck Depression Inventory-II: BDI-II	X		X	X	X	X	X	X	X	X	X
Deployment Risk & Resiliency Inventory-2	X										
Columbia Suicide Severity Rating Scale	X					X				X	X
Penetration of the Blind Questionnaire										X	
AUDIT	X										
Cognitive Testing		X				X				X	
Blame Questionnaire	X									X	
Fagerstrom	X										
Coping Inventory	X									X	
Visual Analog Scale: VAS - fMRI	X									X	
History of Head Injuries BL	X										
History of Head Injuries FU										X	
Satisfaction Questionnaire										X	X
Treatment Services Review	X	X	X	X	X	X	X	X	X	X	X
Neuroimaging Procedures	■										■
Cognitive Behavioral Therapy: CBT			◆	◆	◆	◆	◆	◆	◆	◆	

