**Alcohol/Substance Use Disorder and Craving**

- **Timeline Follow-Back (TLFB; Sobell & Sobell, 1992):** The TLFB obtains retrospective self-report of substance use by using a calendar and memory prompts to stimulate recall. Quantity and frequency assessments are made using this instrument (e.g., total number of standard drink units, percent of days using) as well as abstinence (yes/no). TLFB yields consistently high test-retest correlations and correlates well with other self-reports and collateral reports. The TLFB will assess consumption of alcohol (standard drink units) for 60 days prior to study entry, during the treatment and follow-up phase. Use of nicotine and other drugs of abuse, including prescription drugs, will also be assessed using the TLFB.

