## Protocol: Glial Regulators for Testing Comorbid Posttraumatic Stress Disorder and Substance Use Disorders

- Alcohol Breathalyzer Test will be used to measure blood alcohol concentration (BAC) on a weekly basis for in person visits. Samples reading >0.01 g/dl will be considered positive.
- Alcohol Saliva Test will be used to measure blood alcohol concentration (BAC) on a weekly basis for telehealth visits. In front of the camera, participants will open the one time use test strip, place strip on tongue for 10 seconds, then hold test strip and a color chart to the camera for a study team member to assess. Samples reading >0.01 g/dl will be considered positive.
- Obsessive Compulsive Drinking Scale (OCDS) (Anton et al., 1995): The OCDS is a 14-item self-report measure of craving with high internal consistency and concurrent validity, and good predictive validity of future drinking (Anton et al., 1995; Drobles & Thomas, 1999). It will be used to assess craving.
- Visual Analog Craving Scale (VAS): A Modification of the Within Session Rating Scale (Childress et al., 1986) will be used to assess subjective ratings including craving (amount, frequency), stress and mood, with anchors from 0 = “none” to 10 = “extreme”.
- Visual Analog Scale (VAS) fMRI: A modification of the Within Session Rating Scale (Childress et al., 1986) will be used to assess subjective ratings including craving and stress before and after the fMRI scan.
- Clinical Institute Withdrawal Assessment of Alcohol-Revised (CIWA-Ar) (Sullivan et al., 1989): The CIWA-Ar is a widely used, 10-item clinician administered instrument that will be used to assess alcohol withdrawal symptoms. Subjects experiencing significant withdrawal, as evidenced by a score of  $\geq 10$ , will be assessed by the Study Physician ([name]) and referred clinically for medically supervised detoxification.
- Alcohol Use Disorders Identification Test (AUDIT) (Babor et al., 2001): The AUDIT is a 10-item self-report screening measure, developed by the World Health Organization (WHO), with three subscales (alcohol consumption, drinking behavior, and alcohol-related problems). Items are summed for a total score of 40. The AUDIT has good internal consistency ( $\alpha = .80-.93$ ) as well as sensitivity and specificity.

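### Hypothesis 1 is about AUD/SUD severity and craving, but both of its primary outcomes measure alcohol, and no Hypothesis 1 analysis names the collected drug-use data as an outcome

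*Combined protocol and SAP*

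**What the plan says.** - **Construct.** The Hypotheses section states Hypothesis 1 as a "significantly greater reduction in SUD severity and craving from baseline to end of treatment (week 8"). The Statistical Analyses section repeats it for AUD/SUD severity and craving.
- **Population.** Under Inclusion/Exclusion Criteria, participants must "meet DSM-5 criteria for current AUD/SUD". No criterion requires AUD or any drinking. On diagnosis, "The MINI will be used to diagnose AUD, SUD, and confirm other exclusionary psychiatric diagnoses", so the two disorders are identified separately.
- **Primary outcomes, broad version.** Assessment Instruments lists alcohol/substance use severity measured by TLFB, and craving measured by OCDS.
- **Primary outcomes, analysis version.** The Hypothesis 1 analysis uses "total number of standard drinks consumed and the OCDS total score as the primary outcomes". The OCDS is the Obsessive Compulsive Drinking Scale, credited with "good predictive validity of future drinking".
- **Additional Hypothesis 1 outcomes.** EtG, the percentages of drinking and heavy drinking days, and VAS craving.
- **Drug-use data.** The TLFB yields measures such as "total number of standard drink units, percent of days using) as well as abstinence (yes/no"), and "Use of nicotine and other drugs of abuse, including prescription drugs, will also be assessed using the TLFB". Table 1 schedules "Urine Drug Screen: UDS" at baseline, weeks 4 and 8, and follow-up.
- **Hypothesis 3A.** Prefrontal-amygdala connectivity, at rest and in response to alcohol/drug cues, is to predict change in total standard drinks.

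**The concern.** The measured outcomes cover only part of the hypothesised construct. Two kinds of participant show why this matters.

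- **Drug use disorder only.** These participants have little room to show an effect on drinks or on a drinking-craving scale, whatever happens to their drug use.
- **Both disorders.** A participant may drink less while using more drugs. The primary analysis would score this as improvement, and the plan would call it reduced substance use disorder severity. Such participants are foreseeable: the pilot work cited under Power and Sample Size Estimation was in cocaine dependence with comorbid AUD.

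The hurdle model has a related wording fault. The named outcome is drinks, but the count part is described in terms of days of use, and the zero part is called abstinence without naming a substance. Hypothesis 3A carries the mismatch into imaging: the cue script may describe drug use, while the only named response variable is change in drinks.

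**Working it through.** No figure in the plan bears on coverage, so the check is a comparison of the text.

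**1. Is each measure named for Hypothesis 1 specific to alcohol?**

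| Measure | Role in Hypothesis 1 | Covers drug use or drug craving? |
|---|---|---|
| Total standard drinks | Primary | No |
| OCDS total | Primary | No; a drinking scale, with no drug adaptation described |
| Percent drinking days | Additional | No |
| Percent heavy drinking days | Additional | No |
| EtG | Additional | No; an alcohol metabolite |
| VAS craving | Additional | Substance not stated; measures craving, not use |
| Baseline alcohol/substance use | Covariate only | Possibly, but not an outcome |
| TLFB drug use | Not named as an outcome | Yes |
| Urine drug screen | Not named | Yes |

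The two measures that clearly capture drug use are the two that no Hypothesis 1 analysis uses as an outcome.

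**2. Does the plan agree with itself?** Assessment Instruments gives the primary use outcome as severity of alcohol/substance use by TLFB, which could include drugs. The Hypothesis 1 analysis narrows it to drinks without explanation. The two sections need to be reconciled.

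**3. What would the hurdle model estimate?** It is to be explored if the modelled outcome has excess zeros. With drinks as the outcome, a zero is zero drinks, so abstinence means no alcohol regardless of drug use. This could include drug-only participants and also participants with both disorders who stop drinking but continue using drugs. The count part would model drinks above zero, so describing it as days of use conflicts with the named outcome.

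**4. Hypothesis 3A.** The analysis text names change in total standard drinks as the response, both for resting connectivity and for the alcohol/drug cue. Associations with other alcohol/drug outcomes appear only among the exploratory analyses.

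**5. Illustration for OCDS.** Let p be the drug-only share, equal in both arms, and assume no OCDS effect in those participants. On the scale of mean scores:

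whole-sample difference = (1 − p) × AUD difference + p × 0 = (1 − p) × AUD difference.

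At assumed p of 10%, 20%, 30% and 50%, the whole-sample difference is 0.9, 0.8, 0.7 and 0.5 of the AUD difference. The documents do not give p. If the log-link model is applied to the OCDS, it would report a ratio, whose shrinkage also depends on the mean score of drug-only participants.

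**The case against.** The strongest reply is that the plan is broader than the primary outcomes suggest. Assessment Instruments speaks of alcohol/substance use severity, baseline alcohol/substance use enters the models, the hurdle wording refers to days of use, VAS craving is not tied to alcohol, and the imaging section promises exploratory work on other alcohol/drug outcomes. All of this is in the text, but none of it makes drug use a Hypothesis 1 outcome. The broad wording is not carried into the analysis, the baseline term is a covariate, the hurdle wording belongs to a model whose named outcome is drinks, VAS measures craving, and the exploratory work belongs to imaging. What stands is that the plan does not wholly ignore drug outcomes, and that alcohol conclusions from the alcohol outcomes are unaffected by this point.

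A second reply is that few drug-only participants may enrol. That is possible, but participants with both disorders raise the same problem.

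A reader might also infer three stronger points, which the documents do not support:

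- **A stated loss of power or dilution of the drinks ratio.** This depends on the drug-only share, on how much those participants drink, and on how the mixed model's subject effects weight them. The first two are not given, and the last depends on the fitted model.
- **A stated attenuation of the Hypothesis 3A slope.** This depends on how connectivity differs between drug-only and AUD participants, which is not given.
- **A cap on false abstinence equal to the number of drug-only participants.** Participants with both disorders can also have zero drinks while using drugs.

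**Conclusion.** The point holds as a mismatch between hypothesis and outcomes. As written, a result on drinking and alcohol craving would be read as a result on substance use disorder severity and craving. The wording conflict in the hurdle model and the drinks-only response in Hypothesis 3A belong to the same problem.

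The size is not estimated. The OCDS fractions only illustrate proportional shrinkage under an assumed share, equal between arms, with no OCDS effect in drug-only participants. The conclusion assumes that the OCDS is used as a drinking scale, which follows from its name and description, and that the outcome named in the analysis section governs. It should be fixed before unblinding, because choosing a drug-use outcome afterwards would be open to the charge of being data-driven.

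**What to change.** Before unblinding, reconcile Assessment Instruments with the Hypothesis 1 analysis as follows.

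1. Keep standard drinks and OCDS as alcohol outcomes, limit their conclusions to alcohol, and add an analysis in participants with AUD at baseline.
2. Add a named whole-sample Hypothesis 1 use outcome: the TLFB proportion of observed days using any substance diagnosed by the MINI. Days used cannot exceed days observed, so fit a binomial-type mixed model adjusted for the baseline proportion. State the baseline window for drugs, since the 60-day window is stated for alcohol, and say how nicotine is handled. Report the urine drug screen as support.
3. In Hypothesis 3A, relate connectivity to change in this outcome alongside change in drinks.
4. State which substance hurdle abstinence refers to, and describe the count part of the drinks model as drinks.

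If the drug-use outcome is not added, restate Hypotheses 1 and 3A as alcohol use and alcohol craving, define the AUD analysis set, and drop the substance use disorder conclusion.

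The cost is an amendment to outcome definitions and analysis wording; TLFB drug use and urine screens are already collected. The new outcome must be placed in the outcome hierarchy, and the AUD-only analysis will have fewer participants. The fallback adds no outcome but gives up the broader claim.

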We plan to use REDCap for data capture and management. REDCap (Research Electronic Data Capture) is a software toolset and workflow methodology for electronic collection and management of research and clinical trial data (Harris et al., 2008; Harris et al., 2007). REDCap provides secure, web-based flexible applications, including real time validation rules with automated data type and range checks at the time of entry. Exports are made available for several statistical packages including SPSS, SAS, SATA, R and Microsoft Excel.

**Power and Sample Size Estimation.** It is expected that subjects treated with NAC, as compared to placebo, will exhibit significantly lower PTSD symptoms and craving at week 8. The effect sizes for these analyses ( $d = 1.27$ ,  $d = 1.03$ , respectively) are based on our PoP data. A sample size of 26 would provide power ( $1-\beta$ ) of .80 to detect a large effect size with a Type 1 error protection level of .05 (Cohen, 1988). It is expected that NAC, as compared to placebo, will exhibit significantly lower AUD/SUD severity at week 8. To date, no published studies have examined NAC for the treatment of AUD. Assuming a medium effect size ( $d = .2$ ), with a Type 1 error protection level of .05 and  $(1-\beta) = .80$ , a total sample of 58 would be required. Recent unpublished pilot data conducted by our group examining the effects of NAC vs. placebo on standard number of drinks among patients with cocaine dependence and comorbid AUD ( $n=28$ ) found a statistically significant treatment group effect. With regard to neuroimaging, a recent study of 29 individuals (PTSD=14, controls=15) observed significant differences in PFC-AMY resting state connectivity (Sripada et al., 2012). The effect size for this difference was 0.8 (Cohen's  $d$ ). Thus, power ( $1-\beta$ ) reaches .80 with a total sample size of  $N=26$  (two-tailed,  $\alpha = .05$ ). Another study of 45 cocaine-dependent individuals showed that lower PFC-AMY connectivity at baseline predicted relapse (McHugh et al., 2014). The effect size for this reduction was 1.0. Thus, power ( $1-\beta$ ) reaches .80 with  $N=34$  subjects (two-tailed,  $\alpha = .05$ ).

**Hypotheses:** The hypotheses and statistical approaches for testing each hypothesis are listed below.

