Hypothesis 1: NAC treatment will result in significantly greater reduction in AUD/SUD severity and craving, as compared to placebo. To test this hypothesis, a mixed effects modeling framework will be specified with the

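### Hypothesis 1 assumes Poisson for both standard drinks and the OCDS score, with no rule for overdispersion, so a week-8 test may have the wrong size

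*Combined protocol and SAP*

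**What the plan says.** Under Statistical Analyses, Hypothesis 1, "a mixed effects modeling framework will be specified with the" "total number of standard drinks consumed and the OCDS total score as the primary outcomes". The next sentence reads "A Poisson distribution will be assumed with a logarithm link function to assess the effects of NAC treatment". No other distribution is given for either outcome.

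The plan then notes that "Data collected in substance abuse studies often contain a preponderance of zeros" and adds: "If this excess is present in the distribution, two-part Hurdle models (Poisson and NB) will be explored". Of that model it says "The hurdle part of the model will allow us to estimate the probability of abstinence during the study period". The count part is said to assess the "risk of an increase in using days beyond zero during the study period". NB appears only inside this branch.

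Hypothesis 2, in the same section, gives CAPS-5 a Gaussian mixed model, adjusted for baseline, with residual checks and transformation if needed.

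On timing, the Hypotheses section sets the comparison from baseline to week 8, and the power section expects that NAC "will exhibit significantly lower AUD/SUD severity at week 8". The hurdle text speaks of the study period as a whole.

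**The concern.** - **OCDS.** It is the score of a 14-item questionnaire, not a count of events, so nothing ties its variance to its mean. CAPS-5 is also a severity score and gets a Gaussian model with residual checks. OCDS gets neither.
- **Drinks.** The only exit from Poisson is too many zeros. Counts with few zeros but more week-to-week variation than Poisson allows stay in the Poisson model, and standard errors can then be too small. Entry on AUD/SUD admits participants with a drug disorder only, so zeros may be common. In that case the hurdle route offers Poisson or NB with no rule for choosing, and the Poisson form brings the problem back.
- **Unstated choices.** The plan gives no random effects and no time term, and does not settle whether the test is at week 8 or over the whole period. These decide how large the drinks problem is.

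Both outcomes are primary. At stake is a false-positive rate above the stated .05 that varies with choices still open when the data are seen. A smaller point is that the hurdle count is worded as days of use, although the outcome is standard drinks.

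**Working it through.** The plan gives no mean or variance for drinks or OCDS, so there is no figure of its own to reproduce. The check is the type I error of the week-8 treatment contrast with no true effect.

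**Inputs from the plan.** N = 90, 8 weekly visits with drinks and OCDS recorded at each, baseline value as covariate, type I error .05.

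**Assumed inputs.** 45 per arm, no dropout, mean 20 drinks per week, between-person log SD 0.8, log of 8-week baseline drinking as covariate. Terms: treatment, week, treatment by week. Laplace fit, Wald z test. NB counts of size k = 10, 5 and 2.

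**Step 1: what is at risk.** NB variance is μ + μ²/k, so variance/mean is φ = 1 + μ/k. At μ = 20 this is 3, 5 and 11. If none of it is modelled, the true size is 2{1 − Φ(1.96/√φ)}, which gives .26, .38 and .55. A simulated group-by-time test under a Poisson random intercept gave .37 to .40 at φ = 5, in line with this. The week-8 contrast is partly protected, because the random intercept puts between-person variance into its standard error.

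**Step 2: drinks, few zeros (1% to 7%).** Rejection in %, linear time / week as category. *Stable* means personal levels stay at baseline (400 runs). *Shift* means they move with log SD 0.8 (300 runs). RI is random intercept.

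| Levels, size | Poisson RI | Poisson RI + slope | NB RI | Robust SE | Robust, small-sample |
|---|---|---|---|---|---|
| Stable, 10 | 12.8 / 23.3 | 5.0 / 15.8 | 5.3 / 5.3 | 5.3 / 6.3 | 3.8 / 3.5 |
| Stable, 5 | 17.0 / 28.3 | 4.5 / 18.0 | 3.8 / 5.5 | 5.3 / 7.0 | 4.5 / 4.5 |
| Stable, 2 | 20.8 / 38.5 | 5.0 / 21.5 | 4.0 / 4.8 | 6.5 / 8.5 | 5.5 / 4.5 |
| Shift, 10 | 6.3 / 10.3 | 6.0 / 9.3 | 6.0 / 6.0 | 5.3 / 7.0 | 4.0 / 3.3 |
| Shift, 5 | 9.3 / 11.0 | 6.0 / 8.7 | 6.3 / 5.0 | 6.3 / 7.0 | 6.0 / 4.3 |
| Shift, 2 | 14.7 / 22.7 | 9.0 / 17.0 | 8.0 / 5.7 | 8.7 / 8.0 | 7.3 / 5.3 |

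A control without overdispersion gave 7.0 / 6.0. An effect averaged over weeks gave 5.0 to 9.3, and one total per person 5.0 to 8.0. The control gave 9.0 for each of these, so Poisson adds no harm there. Monte Carlo SE at 5% is 1.3 points (300 runs) or 1.1 (400).

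**Step 3: drinks with abstinence, sizes 5 and 2 (300 runs).**
- 20% of participants abstinent throughout (21% to 23% zeros): single Poisson RI 5 to 9%. Hurdle count part: Poisson 19 to 24% (linear) or 27 to 41% (category), NB 4 to 6%.
- 20% of weeks abstinent (21% to 22% zeros): hurdle Poisson 20 to 32%, hurdle NB 3 to 8%. A single NB model is conservative at 1 to 4%.

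The zero part of the hurdle model was not simulated.

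**Step 4: OCDS (assumed mean 20, between-person SD 6, 500 runs).** Poisson implies a within-person SD of √20 = 4.47.

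| True within-person SD | 4.47 / SD | Poisson RI | Gaussian |
|---|---|---|---|
| 3 | 1.49 | 3.0 / 0.8 | 6.0 / 3.6 |
| 5 | 0.89 | 5.0 / 5.8 | 4.0 / 4.0 |
| 7 | 0.64 | 9.4 / 11.0 | 6.4 / 4.6 |

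**Step 5: separate fits.** A gamma random intercept with closed-form likelihood, stable levels, 400 runs, gave 3 / 5 for the control and 13 / 24, 20 / 31 and 25 / 42 for sizes 10, 5 and 2. Its shifting-level runs are set aside because their control was already 13%. Another Laplace random-intercept run with linear time (200 runs per cell) gave 26 and 25 for sizes 5 and 2 (stable) and 9 and 16 (shift), with NB at 5 to 8.

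**The case against.** - **The stable scenario flatters the concern.** With those inputs, baseline drinking explains about 96%, 94% and 89% of between-person variance in log level (sizes 10, 5, 2), which leaves the random intercept little to absorb. All participants receive weekly CBT, so levels should move. When they do, baseline explains about 45% to 48%. This stands as a reason to read the stable figures as the upper end. It does not remove the problem: under shift the random-intercept model still gives 6 to 15% (linear) and 10 to 23% (category).
- **A mixed model absorbs much of the overdispersion.** A simulation without the baseline covariate kept the linear-time contrast at .043 to .077 when between-person CV was 1 or more. The assumed log SD of 0.8 is a CV of √(exp(0.64) − 1) = 0.95. With week as a category it gave .10 to .21 at φ = 5. That is fair, but the plan does adjust for baseline use, which shrinks that spread. At CV about .3 the same simulation reached .18 (linear) and .30 (category) at φ = 10.
- **A whole-period reading shows no harm.** This stands. The hypotheses and the power section nevertheless name week 8.
- **The plan expects many zeros, and NB is listed.** With whole-period abstainers the single Poisson model is near nominal. But that is when the hurdle route opens, and its Poisson form is equally permitted.
- **The OCDS harm is small and of unknown direction.** This stands. That part rests on model fit and on consistency with CAPS-5, not on a large error.
- **Some excess may come from the Wald test.** This is true of the averaged and total tests, whose control was 9%. The week-8 control of 6 to 7% cannot explain rates of 20% and above.

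**Conclusion.** The concern holds as a conditional one. The plan fixes Poisson for both outcomes, lets only excess zeros change it, and has no rule for overdispersion. If drinks are tested at week 8 and vary within person more than Poisson allows, a random-intercept model can reject a true null at well above 5%: up to 21% with linear time and 39% with week as a category under the inputs in Step 2. A random slope removes most of this with linear time (5 to 9%) but not with week as a category (9 to 22%). NB or robust inference stays near nominal in the same settings. A whole-period effect is not harmed. For OCDS the error runs from about 1% to 11%, depending on a within-person SD the plan does not give.

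The sizes rest on an assumed drinking mean, spread and overdispersion, so the direction for drinks is firmer than any single percentage. It should be corrected before the data are analysed.

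**What to change.** 1. **OCDS:** analyse the total with the Gaussian mixed model planned for CAPS-5, adjusted for baseline OCDS, with the same residual checks.
2. **Drinks:** commit in advance to one approach that tolerates overdispersion. Either use an NB mixed model when zeros are not in excess and the NB form of the hurdle model when they are, or use participant-level robust standard errors with a small-sample correction. Define excess zeros beforehand, for example by comparing the observed share of zeros, pooled over arms, with the share the fitted NB model predicts.
3. **Supporting wording:** state the random effects, how time enters, and whether the primary test is the week-8 contrast or the whole-period effect. Name standard drinks as the hurdle count.

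The cost is a few sentences and minor programming, with no new data. Intervals for drinks will usually be wider, and a single NB model loses some power if abstinent weeks are scattered (1 to 4% rejection in Step 3), which is why the rule for zeros has to be set in advance.
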